8.4. Statistical Analysis

Descriptive and/or summary statistics will be calculated for the primary endpoints, which are the user touch and feel experience of the hand sanitizer products evaluated by visual analog scale assessments of HCWs overall satisfaction and moisturization, and HCWs assessment of product preference. Statistical analyses will be conducted in SAS® software, Version 9.4 or higher of the SAS System for Windows (Copyright © 2013 SAS Institute Inc.) or other appropriate statistical software.

All continuous variables will be summarized using the following descriptive statistics: n (non-missing sample size), mean, standard deviation, median, maximum and minimum. The frequency and percentages (based on the non-missing sample size) of observed levels will be reported for all categorical measures. In general, all data will be listed, sorted by site, treatment and subject, and when appropriate by visit number within subject. All summary tables will be structured with a column for each treatment in the order (Control, Experimental) and will be annotated with the total population size relevant to that table/treatment, including any missing observations.

All protocol deviations will be recorded and examined for potential bias in accordance with section 9.

8.4.1 Assessment of Satisfaction and Moisturization

HCWs' overall satisfaction of the interventions will be evaluated for each intervention using a VAS scale in millimeters. Summary statistics will be calculated for the VAS score by intervention for each statement in the survey. The satisfaction scores will be compared across the two interventions using either ANOVA/t-tests or another method, as appropriate for the data distribution.

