6.1.3. Hand Sanitizer A Application and Touch and Feel Assessment

Study staff will be provided with hand sanitizers and dispensers to use prior to handling any items such as product bottles, pens, or paperwork, for the duration of the study activities.

Participants will first be asked to wash and dry their hands and wait an additional two minutes after their hands have dried before application of the hand sanitizer products. Study staff will use a stopwatch set for two minutes to ensure participant compliance to the two minute waiting period after hand washing. The participants will be instructed by study staff to apply one automatically dispensed amount, approximately 1 mL, of the first product (Hand Sanitizer A) topically to their hands and rub the product until the product is absorbed. The order in which each product is applied will be randomized. After product application, the participants will complete a VAS assessment of their touch and feel experience with Hand Sanitizer A, which will include questions regarding the participant's perceived moisturization and overall satisfaction with the hand sanitizer. Participant responses to the assessment will be recorded in the CRF by study staff.

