6.1.4. Hand Sanitizer B Application and Touch and Feel Assessment

The participant will again be asked to wash their hands with soap and water and dry their hands and wait an additional two minutes after their hands have dried. Study staff will again time the two minute waiting period using a stopwatch. The participant will then repeat the described application process with the second product (Hand Sanitizer B), as the participants will be instructed by study staff to apply one automatically dispensed amount of approximately 1 mL of Hand Sanitizer B topically to their hands and rub the product until the product is absorbed. After product application, the participant will complete a VAS assessment of their touch and feel

experience with Hand Sanitizer B. Participant responses to the assessment will be recorded in the CRF by study staff.

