8. STATISTICAL CONSIDERATIONS

8.1. Sample Size Determination

Sample size N of 90 (45 for a foam cohort and 45 for a gel cohort to be evaluated in a future study) was estimated to provide 80% power at the 95% level of significant for the proportion of HCW preferring one gel/foam product over the competing gel/foam product using the "Non-Inferiority Tests for the Difference Between Two Correlated Proportions" procedure in PASS 2021 Power Analysis and Sample Size Software (2021). NCSS, LLC. Kaysville, Utah, USA, ncss.com/software/pass. The estimated non-inferiority margins were .03 to .08 with estimated proportion differences of .1, .15 and .20. This study will utilize the sample of N=45 for the foam cohort.

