8.2. Randomization

The order in which the participants test a hand sanitizer product first or second will also be randomly assigned. The participants, as well as on-site staff will be blinded to testing products. If a participant is unable to complete the study or has missing data, the participant will be replaced such that the new participant will be assigned to the randomization cohort of the replaced participant. Randomization schedule will be generated using SAS® software, Version 9.4 of the SAS System for Windows. Copyright © 2013 SAS Institute Inc.

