8.3. Populations for Analyses

The analyses will be performed on the intent-to-treat population which consists of all subjects who were qualified for entry criteria and adhered to the protocol, meaning completing the satisfaction and user experience questionnaire for both testing products.

No per protocol, safety, or other analyses groups are planned.

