8.4.2 Assessment of Product Preference

A product preference questionnaire will be filled out by the participants after testing both hand sanitizer products. The proportion of participants showing preference of the sanitizer products will be compared within each cohort using McNemar Test for Two Correlated Proportions or other appropriate methods, depending on the distribution of data.

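### Section 8.4.1 does not say that the VAS comparison is within participant and has no term for the randomised order; stating both would be a cheap improvement

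*Combined protocol and SAP*

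**What the plan says.** All references are to the combined protocol and SAP.

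- **VAS comparison (8.4.1).** After promising summary statistics by product, the section says: "The satisfaction scores will be compared across the two interventions using either ANOVA/t-tests or another method, as appropriate for the data distribution". It mentions neither pairing nor repeated measures, and it has no order, period or sequence term.
- **Endpoints (8.4).** The primary endpoints are "evaluated by visual analog scale assessments of HCWs overall satisfaction and moisturization", together with product preference. The comparison sentence in 8.4.1 names satisfaction only, although the section's title also covers moisturization.
- **Analysis set (8.3).** Inclusion requires "completing the satisfaction and user experience questionnaire for both testing products", so every analysed participant contributes a pair of scores.
- **Randomisation (8.2).** "The order in which the participants test a hand sanitizer product first or second will also be randomly assigned". No allocation ratio or blocking is given here or in 6.1.2.
- **Position (6.1.3, 6.1.4).** Participants apply "the first product (Hand Sanitizer A) topically to their hands". Before the second product they "wash their hands with soap and water and dry their hands and wait an additional two minutes after their hands have dried". The labels A and B therefore mark position, and period is known for every score.
- **Preference (8.1, 8.4.2).** The sample size uses "Non-Inferiority Tests for the Difference Between Two Correlated Proportions" and the analysis uses "McNemar Test for Two Correlated Proportions or other appropriate methods, depending on the distribution of data". Both treat the data as correlated.
- **Other variables (8.4.3).** Only age and sex are named, for secondary analysis.

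**The concern.** Whether scores are paired is fixed by the design, and the shape of the data cannot decide it. Section 8.4.1 makes the data distribution the only criterion for choosing a method, so the text as written would permit an independent-samples t-test on paired scores. If the two scores from one person are positively correlated, that test gives too wide an interval.

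The second gap is order. It is the one factor the trial randomises, yet the VAS analysis does not use it. If the second product tends to be scored higher or lower than the first, this has two effects on an unadjusted paired analysis. The order effect inflates the variance of the within-person differences. It also shifts the estimated product difference whenever the two orders are unequal in number. With 45 participants the orders cannot be exactly equal, and without a stated ratio or blocking they could be clearly unequal.

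At stake is the precision, and to a lesser extent the bias, of the two VAS comparisons among the primary endpoints.

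**Working it through.** **Inputs from the documents.** N = 45, each participant rating both products (8.1, 8.3); random order (8.2). The only planning figure, 80% power, concerns preference. It cannot be reproduced uniquely because the proportion of discordant pairs is not stated, and this point does not depend on it. There is no VAS planning figure to reproduce.

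**Assumptions.** Units are the SD of one VAS score for a given product and position. Within-person correlation ρ = .3, .5 or .7. Order effect (second position minus first) d = 0, 0.2 or 0.5 SD. Order split n₁/n₂ = 23/22, with 20/25 and 18/27 as less even cases.

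**1. 95% CI half-widths with no order effect, split 23/22**

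- Independent samples: t(88) × √(2/45) = 1.987 × 0.2108 = 0.419.
- Paired: t(44) × √(2(1−ρ)/45), with t(44) = 2.0154.
- Within participant with period: t(43) × √(2(1−ρ)) × ½√(1/n₁ + 1/n₂), with t(43) = 2.0167.

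| ρ | Independent | Paired | With period | Independent ÷ with period |
|---|---|---|---|---|
| .3 | 0.419 | 0.355 | 0.356 | 1.18 |
| .5 | 0.419 | 0.300 | 0.301 | 1.39 |
| .7 | 0.419 | 0.233 | 0.233 | 1.80 |

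The paired and period-adjusted columns are almost equal, so stating that the test is paired secures nearly all of this gain.

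**2. What the period term adds to a paired test, split 23/22.** An order effect d adds 4d²n₁n₂/(45 × 44) to the variance of the unadjusted differences. The period-adjusted interval is unaffected.

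| d | Paired half-width, ρ = .3/.5/.7 | Period-adjusted interval narrower by |
|---|---|---|
| 0.2 SD | 0.361 / 0.307 / 0.241 | 1.3 / 1.9 / 3.2% |
| 0.5 SD | 0.387 / 0.337 / 0.278 | 8 / 11 / 16% |

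**3. Bias from unequal orders.** Given the realised split, the unadjusted mean difference is shifted by |n₁ − n₂|/45 of the period difference: 1/45 = 2% at 23/22 and 9/45 = 20% at 18/27. With d = 0.2 SD, the shift at 18/27 is 0.20 × 0.2 = 0.04 SD. Under simple randomisation, the probability of a split at least as uneven as 18/27 is 2 × P(Bin(45, ½) ≤ 18) = 0.23.

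**4. Cost with no order effect.** Degrees of freedom fall from 44 to 43. The ratio of the period-adjusted to the paired interval is (2.0167/2.0154) × ½√(1/n₁ + 1/n₂) ÷ √(1/45), where √(1/45) = 0.14907:

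| Split | ½√(1/n₁ + 1/n₂) | Interval wider by |
|---|---|---|
| 23/22 | 0.14911 | 0.1% |
| 20/25 | 0.15000 | 0.7% |
| 18/27 | 0.15215 | 2.1% |

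**5. Carryover.** If the effect of the first product persists, both the adjusted and the unadjusted product difference are biased by half the difference in carryover between the products. The period term does not remove this.

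**The case against.** The strongest reply is that pairing is already implied. Section 8.4.1 admits a paired t-test or a repeated-measures ANOVA, the preference analysis is explicitly for correlated data, and the analysis set requires ratings of both products. A competent analyst would probably pair. This stands. The 1.18 to 1.80 ratios describe a test that is permitted but unlikely, and an independent-samples test on positively correlated scores would err on the conservative side.

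It is also fair that the precision gain from the period term is modest. At 0.2 SD it is a few per cent, and nothing in the documents supports an order effect as large as 0.5 SD. At an 18/27 split with d = 0.2 SD, the adjusted interval is even slightly wider, by 0.7% and 0.2% at correlations of .3 and .5, and is 1.1% narrower at .7. At that same split, however, the unadjusted estimate carries the 20% shift, so the comparison of widths is not the whole case.

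The omission of moisturization from the comparison sentence may be shorthand, since the section title includes it and the summaries cover every survey statement.

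Three stronger readings are tempting and are not supported:

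- **That the plan specifies an unpaired test, or that the trial will lose substantial power.** The text leaves the method open.
- **That a crossover model would bring order into all of Section 8.4.** It leaves the McNemar preference analysis in 8.4.2 without order, and that would need its own stratified version.
- **That the change would allow a VAS non-inferiority conclusion.** The documents set no VAS margin, and a better interval does not supply one.

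**Conclusion.** The point holds as a cheap improvement to the VAS comparison; it does not show an error in the plan. Section 8.4.1 states neither that the comparison is within participant nor that it uses the randomised order, and the criterion it gives cannot settle pairing. Most of the benefit lies in removing the option of an independent-samples test. The further benefit of adjusting for order is a small gain in precision if order effects are modest, and protection against a shift in the estimate if the orders turn out uneven. Every size quoted depends on the assumed correlation, order effect and split, because the documents give none of these. The conclusion that the change costs little holds over the splits shown: at most 2.1% in interval width at 18/27, and 0.1% near an equal split.

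**What to change.** In Section 8.4.1, for the VAS comparison only:

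1. State that overall satisfaction and moisturization are each compared within participant, with order as a factor. Use a model with product, period and sequence as fixed effects and participant as random effect, or the equivalent analysis of within-person differences by sequence.
2. Report the Spectrum minus Purell difference with its 95% CI for each of the two items.
3. Name in advance a rank analysis of within-person differences by sequence as the fallback for clearly non-normal differences.
4. State that the estimate assumes no differential carryover after the wash and two-minute wait. This design cannot test that assumption, because carryover is confounded with sequence.

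The cost is a few sentences in 8.4.1, a few lines of SAS and one degree of freedom against a paired test. No new data, participants, procedures or randomisation change are needed. If only a minimal edit is acceptable, stating that the test is paired for both items secures most of the gain in precision, but it leaves the estimate exposed to a shift from uneven orders.

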8.4.2 Assessment of Product Preference

A product preference questionnaire will be filled out by the participants after testing both hand sanitizer products. The proportion of participants showing preference of the sanitizer products will be compared within each cohort using McNemar Test for Two Correlated Proportions or other appropriate methods, depending on the distribution of data.

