The sample size of 90 (45 for the foam cohort and 45 for a gel cohort to be evaluated in a future study) was estimated to provide 80% power at the 95% level of confidence for the proportion of HCWs preferring one product over the competing product using the "Non-Inferiority Tests for the Difference Between Two Correlated Proportions" procedure in PASS 2021 Power Analysis and Sample Size Software (2021). NCSS, LLC. Kaysville, Utah, USA, ncss.com/software/pass. The estimated non-inferiority margins were .03 to .08 with estimated proportion differences of .1, .15 and .20. This study utilizes the sample of N=45 for the foam product cohort.

Description of Sites/Facilities Enrolling Participants: Description of Study design: The study will be conducted at Northshore Hospitals.

This will be a prospective, single-blinded randomized cohort study that will be conducted over the course of one study visit. Participants will be asked to wash and dry their hands and apply a sanitizer product. The order in which the two hand sanitizer products are applied will be randomized. The participants will be instructed to apply the product topically to their hands and rub the product until the product is absorbed. After product application, the participants will complete a VAS assessment of their touch and feel experience with the product. Participants will then repeat the process with the second product. In the time between evaluating each product, participants will be asked to wash and dry their hands with soap and water and wait an additional two minutes after their hands have dried. After applying both products, the participants will complete a product preference questionnaire.

Participant Duration:

Approximately one hour.

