3. OBJECTIVES AND ENDPOINTS

OBJECTIVES	ENDPOINTS	JUSTIFICATION FOR ENDPOINT(S)
Primary		
1. To establish the non-inferiority of the Spectrum product to the Purell product by comparing the foam hand sanitizers with regard to the user touch and feel experience and overall acceptability.	1. The user touch and feel experience of the hand sanitizer products evaluated by VAS assessments of HCWs overall satisfaction and moisturization, and HCWs assessment of product preference.	To evaluate the HCW user touch and feel experience of the products and compare product preference between the foam hand sanitizer products.

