6.1.5. End of Study Activity: Product Preference Questionnaire

After applying the two foam Hand Sanitizers A and B, the participant will complete a Product Preference Questionnaire. Participant responses to the questionnaire will be recorded in the CRF by study staff. When both Hand Sanitizers A and B have been applied and the participant has completed the study VAS Assessments and the Product Preference Questionnaire, the participant will be dismissed from the study.

7. ADVERSE EVENTS (AEs)

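### Product preference, most likely one comparative answer per participant, is sized and tested as two correlated proportions, and the named McNemar test gives no result on the scale of the non-inferiority margins

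*Combined protocol and SAP*

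**What the plan says.** - **Objective (section 3).** Non-inferiority of Spectrum to Purell is to be established "by comparing the foam hand sanitizers with regard to the user touch and feel experience and overall acceptability". The endpoints listed beside it are VAS overall satisfaction, VAS moisturization and product preference.
- **Collection (6.1.5).** "After applying the two foam Hand Sanitizers A and B, the participant will complete a Product Preference Questionnaire". The VAS form, by contrast, is completed separately after each product (6.1.3, 6.1.4).
- **Sizing (Synopsis and 8.1).** The calculation is "for the proportion of HCWs preferring one product over the competing product", using the procedure "Non-Inferiority Tests for the Difference Between Two Correlated Proportions". Margins run from .03 to .08 and assumed differences are .1, .15 and .20. A total of 90 across a foam and a gel cohort "was estimated to provide 80% power at the 95% level of significant" (the Synopsis says confidence), and "This study will utilize the sample of N=45 for the foam cohort".
- **Analysis (8.4.2).** "The proportion of participants showing preference of the sanitizer products will be compared within each cohort using McNemar Test for Two Correlated Proportions". The same sentence leaves room for an unnamed alternative, to be chosen once the data distribution is known.

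The plan gives no response options for the preference item, no definition of the two-by-two table, no discordant proportion, no sidedness and no single margin.

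**The concern.** Two correlated proportions normally come from a yes/no answer by each participant about each product. A choice between two products is different: preferring Spectrum and preferring Purell are two sides of one answer. Nobody can be a yes for both, and everyone who names a product falls in a discordant cell.

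Two consequences follow. First, the variance of a paired difference grows with the discordant proportion, and a forced choice sets that proportion at its maximum of 1. A sample size that assumed less would be too small. Second, McNemar tests whether the two preference counts are equal. It uses no margin and discards participants with no preference, although those answers are evidence that the products are similar, which matters for a non-inferiority claim.

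A separate, smaller gap is that the objective names overall acceptability and no endpoint is tied to it.

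**Working it through.** **Inputs.** From 8.1: N = 45 (foam), power 80%, margin M from .03 to .08, difference d = .10, .15 or .20. Assumptions: d favours Spectrum; the 95% level means one-sided 5%, with one-sided 2.5% as a second reading. ψ is the total discordant proportion. If every participant names a product, ψ = 1; if no-preference answers are allowed, ψ = 1 minus their share.

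**Step 1: can N = 45 be reproduced?** Not uniquely, because ψ, the sidedness and one pair (d, M) are not given. The paired Wald formula is

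n = (z₁₋α + z₀.₈₀)² (ψ − d²)/(d + M)², with (1.645 + 0.842)² = 6.18 at one-sided 5%.

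Solved for the discordance at which 45 gives 80% power: ψ = 45(d + M)²/6.18 + d².

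- d = .10, M = .03: 45 × .0169/6.18 + .01 = .133
- d = .20, M = .08: 45 × .0784/6.18 + .04 = .611

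Even in the most favourable scenario about 39% of participants (1 − .611) would have to be concordant, that is, state no preference.

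**Step 2: power at N = 45 when everyone names a product (ψ = 1).** Wald power = Φ[(d + M)√45/√(1 − d²) − 1.645]. The exact check treats the number choosing Spectrum as binomial, with null p₀ = (1 − M)/2 and alternative p₁ = (1 + d)/2. At one-sided 5% Spectrum must be chosen by at least 28 of 45 for M = .03 (p₀ = .485) and 27 of 45 for M = .08 (p₀ = .46).

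| d | M | ψ at which 45 gives 80% | Wald power, ψ = 1 | Exact power, ψ = 1 | Wald N for 80%, ψ = 1 |
|---|---|---|---|---|---|
| .10 | .03 | .13 | 22% | 21% | 363 |
| .10 | .08 | .25 | 33% | 30% | 189 |
| .15 | .03 | .26 | 34% | 31% | 187 |
| .15 | .08 | .41 | 47% | 43% | 115 |
| .20 | .03 | .43 | 47% | 44% | 113 |
| .20 | .08 | .61 | 61% | 56% | 76 |

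At one-sided 2.5%, exact power is 13% to 44%, the required ψ is .11 to .49, and the Wald N is 97 to 460. No stated pair reaches 80% at 45 under either reading.

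**Step 3: what McNemar gives on single-choice data.** With b choosing Spectrum and c choosing Purell, the statistic is (b − c)²/(b + c). For b = 28, c = 17 it is 121/45 = 2.69. The sign test gives the same: [(28 − 22.5)/√(45/4)]² = 2.69. So the test is valid, but as a test of equality.

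Compare the net difference D = (b − c)/45 and its one-sided 95% Wald lower bound D − 1.645√((1 − D²)/45), taking all 45 to have chosen:

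- 28 v 17: McNemar 2.69; D = .244; bound .244 − 1.645 × .145 = .007, above both −.03 and −.08.
- 25 v 20: McNemar 25/45 = 0.56; D = .111; bound .111 − 1.645 × .148 = −.133, below both.

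Both statistics are below 3.84 (two-sided 5%, one degree of freedom), so McNemar returns the same verdict. On the margin scale the conclusions are opposite.

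**Step 4: truly equal products (d = 0).** With forced choice, the exact chance of meeting the rule in Step 2 is 6.8% (M = .03) or 11.6% (M = .08). If 40% state no preference (assumed) and stay in the denominator, Φ(M/√(.6/45) − 1.645) gives about 8% and 17%.

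**The case against.** Four points can be made for the plan.

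1. **The test is calculable.** A reader might infer that the planned comparison has no data to work on. The documents do not support that: the preference counts serve as the discordant cells, McNemar becomes a valid sign test, and 8.4.2 also allows other methods. This stands. But the alternative is unnamed and left to the data distribution, and nothing in 8.4.2 refers to a margin.

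2. **The form is not shown.** A questionnaire completed once can hold several items or a no-preference option. This also stands: one answer per participant is a strong inference from the timing and from how the Synopsis describes the sized quantity, not a stated fact. The power figures are therefore conditional on forced choice.

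3. **Acceptability may be covered.** A reader might infer that it goes unmeasured. VAS overall satisfaction is collected for each product and could serve, and 8.4.1 refers to survey statements that are not shown. What is missing is a sentence making the link.

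4. **The sample size assumed a difference in favour of one product, not equality.** True, so the low figures at d = 0 are not the plan's own scenario. The 21% to 56% range uses the plan's own differences and is still below 80%. Nor can the 80% be rescued by attaching it to the total of 90: 8.4.2 compares within each cohort, and this study uses 45.

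**Conclusion.** The concern holds as a mismatch between the measure, the test and the margins. A preference questionnaire completed once most likely yields one answer per participant, while 8.1 and 8.4.2 treat it as two correlated proportions. McNemar on such data tests equal preference only and cannot support non-inferiority on a .03 to .08 difference scale.

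If every participant names a product, exact power at 45 is about 21% to 56% at one-sided 5%, or 13% to 44% at one-sided 2.5%. The stated 80% requires a discordant proportion of about .13 to .61 at one-sided 5%, which the plan neither states nor justifies. These figures assume forced choice and a difference in Spectrum's favour; the sidedness is also an assumption.

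A reader might further infer that correcting the analysis would let the trial show non-inferiority between equally liked products. It would not: Step 4 gives about 7% to 12% with forced choice and about 8% to 17% with 40% no preference. The gain is an analysis that answers the stated question with honest precision.

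**What to change.** Before the data are analysed:

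- **8.4.2.** Describe the preference item and its response options. Analyse it as one multinomial answer: (number preferring Spectrum − number preferring Purell)/all respondents, with any no-preference answers kept in the denominator. Report a confidence interval and compare its lower bound with one pre-specified margin. State the level and sidedness. McNemar may stay as a supportive test of equal preference.
- **8.1.** State the assumed discordant proportion and the single (d, M) pair, and restate the power that N = 45 gives for this measure. The paired formula in Step 1 still applies once the right ψ is entered.
- **Section 3.** Name VAS overall satisfaction as the measure of overall acceptability, or remove that term from the objective.

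The cost is a few sentences in three sections, with no new participants, visits or form items. The sponsor must commit to one margin and will probably have to report less than 80% power. Adding a yes/no acceptability item for each product, or requiring a no-preference option, is a debatable trade-off and is not needed for this correction.

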1. PROTOCOL SUMMARY

1.1. Synopsis

Title:

Touch and Feel Evaluation of Two Foam Hand Sanitizers

Study Description:

Hand sanitizers are a standard of hygiene requirements. Hand sanitizers must be effective at reducing germ count on the hands while ideally providing emollients to moisturize the skin after use. To improve compliance with hand sanitizing protocols, hand sanitizers should provide a pleasant touch and feel experience for end users, especially for healthcare worker (HCW) users, who use these products frequently.

The goal of this study is to evaluate the user experience of two foam hand sanitizers produced by Medline and GOJO when used by HCWs.

The foam sanitizer products that will be evaluated in this study include:

- ➤ SpectrumTM Advanced Hand Sanitizer Foam (hereby referred to as the Spectrum product)
- > PURELL® Advanced Foam Hand sanitizer (hereby referred to as the Purell product)

Phase: Post-market.

Primary Objective: To establish the non-inferiority of the Spectrum product to the Purell product

by comparing the foam hand sanitizers with regard to the user touch and feel

experience and overall acceptability.

Primary Endpoint: The user touch and feel experience of the hand sanitizer products evaluated

by visual analog scale assessments (VAS) of HCWs overall satisfaction and

moisturization, and HCWs assessment of product preference.

Study Population: Number of participants, N = 45.

Inclusion criteria

Individuals who meet the following criteria will participate in this study:

 \rightarrow HCWs \geq 18 years of age.

Exclusion criteria

MED-2022-DIV60-001 18-NOV-2022 Version 3.0

Individuals who meet any of the following criteria will not be allowed to participate in this study:

- Individual has a skin condition that might result in irritation from the hand sanitizers.
- ➤ Individual has a known allergy to the ingredients in the test products.

Power Analysis Methods:

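### The trial aims and is sized for non-inferiority, but section 8.4 names only tests of no difference and sets no margin, one-sided alpha or decision rule

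*Combined protocol and SAP*

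**What the plan says.** The Synopsis (section 1.1) and section 3 give one primary objective: "To establish the non-inferiority of the Spectrum product to the Purell product". The endpoint has three parts: VAS overall satisfaction, VAS moisturization and product preference. None is singled out as the deciding measure.

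Section 8.1 sizes the trial on preference with the procedure "Non-Inferiority Tests for the Difference Between Two Correlated Proportions", claiming "80% power at the 95% level of significant for the proportion of HCW preferring one gel/foam product over the competing gel/foam product". The Synopsis words the error level differently: "80% power at the 95% level of confidence for the proportion of HCWs preferring one product over the competing product". Neither says whether it is one- or two-sided. On margins, section 8.1 states: "The estimated non-inferiority margins were .03 to .08 with estimated proportion differences of .1, .15 and .20". The direction of those differences is not stated.

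Section 8.4 opens with "Descriptive and/or summary statistics will be calculated for the primary endpoints". For the VAS, section 8.4.1 says: "The satisfaction scores will be compared across the two interventions using either ANOVA/t-tests or another method, as appropriate for the data distribution". For preference, section 8.4.2 says the proportions will be "compared within each cohort using McNemar Test for Two Correlated Proportions or other appropriate methods, depending on the distribution of data". The word non-inferiority does not occur anywhere in section 8.4.

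**The concern.** McNemar's test, and ANOVA or t-tests as ordinarily run, take no difference as the null hypothesis. Failing to reject that null is not evidence that Spectrum is no worse than Purell by more than a margin, least of all with 45 participants. Rejecting it in favour of Spectrum shows more than the objective asks for. The plan is silent on the outcomes in between, where a non-inferiority trial is normally decided.

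Three things follow. A non-significant result has no defined reading and could be presented as success. A trial that a proper non-inferiority test would pass can fail under McNemar. With the margin left as a range and alpha without a side, a borderline verdict can be settled after the data are known.

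**Working it through.** **Inputs.** From section 8.1: N = 45, power 80%, margins m from .03 to .08, differences d of .10, .15 and .20. Not in the documents, so varied: the share ψ of participants who state a preference, the sidedness of alpha (one-sided 5% and 2.5% both tried) and the direction of d. I take d as the proportion preferring Spectrum minus the proportion preferring Purell.

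**1. Can the plan's own N be reproduced?** If the differences favour Spectrum, the Wald sample-size formula is n = (ψ − d²)·[(z_α + .842)/(d + m)]². Setting n = 45 gives the largest ψ at which 80% power holds:

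ψ = 45·[(d + m)/(z_α + .842)]² + d²

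- m = .03, d = .10, one-sided 5%: 45·(.13/2.487)² + .01 = .13
- m = .08, d = .20, one-sided 5%: 45·(.28/2.487)² + .04 = .61
- The same two cases at one-sided 2.5%: .11 and .49

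So 45 is attainable for some ψ, but the stated inputs do not determine it. It is unverifiable, not shown to be wrong.

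**2. Non-significance read as non-inferiority.** This is exact trinomial enumeration at N = 45. With b preferring Spectrum and c preferring Purell, McNemar (uncorrected) is non-significant when (b − c)²/(b + c) < 3.841. The non-inferiority test passes when the Wald lower bound exceeds −m, with D = (b − c)/45 and SE = √[(b + c) − (b − c)²/45]/45. At a true deficit of .08:

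| ψ | McNemar non-significant | False pass, m = .08, one-sided 5% | Same, 2.5% |
|---|---|---|---|
| .13 | 69% | 7.9% | 5.5% |
| .21 | 81% | 6.4% | 4.0% |
| .30 | 85% | 5.4% | 3.3% |
| .50 | 88% | 5.1% | 2.9% |
| 1.0 | 94% | 4.2% | 2.1% |

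At a true deficit of .20, McNemar is non-significant in 5% (ψ = .21), 28% (.30), 41% (.40), 50% (.50) and 77% (1.0) of trials. The risk at that deficit therefore depends heavily on ψ.

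**3. Trials that McNemar misses.** True difference +.15 (direction assumed), one-sided 5%:

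| ψ | McNemar favours Spectrum | Non-inferiority passes, m = .03 | m = .08 |
|---|---|---|---|
| .30 | 45% | 76% | 90% |
| .50 | 31% | 55% | 72% |
| 1.0 | 14% | 31% | 43% |

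**4. Leaving margin and alpha open.** Suppose all 45 state a preference.

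- A 28 to 17 split: D = 11/45 = .244 and SE = √(45 − 121/45)/45 = .1445. The lower 97.5% bound is .244 − 1.96 × .1445 = −.039, which passes at .08 and fails at .03. McNemar p = .10.
- A 27 to 18 split: D = .200 and SE = .1461. The bound is −.040 at one-sided 5% and −.086 at 2.5%. At margin .08 it passes at the first level and fails at the second.

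For any number stating a preference from 10 to 45, only one or two splits change verdict between margins .03 and .08. Those splits are not rare, though. At d = +.15 and one-sided 5%, subtracting the last two columns in step 3 (before rounding) gives 14%, 17% and 11% of trials at ψ = .30, .50 and 1.0.

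**The case against.** The best defence is that section 8.4 is open rather than wrong. Both subsections allow other methods, a t-test against a shifted null is a standard non-inferiority test, and section 8.1 names a paired non-inferiority procedure. This shows that a non-inferiority analysis is permitted. It does not show that one is planned: the alternatives are chosen by the distribution of the data and not by the hypothesis, and no such test can be run without one margin and one alpha.

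Second, nothing in the plan says that a non-significant result will be called non-inferior. That stands. The 69% to 94% figures describe what the missing rule leaves possible and are not an error rate of the plan.

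Third, the size rests on an unknown preference share. If the questionnaire forces a choice, only the ψ = 1.0 rows apply. That also stands, but the mismatch is present in every row.

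Two cautions apply to the remedy. The Wald bound runs above its nominal level when few state a preference (7.9% and 5.5% at ψ = .13). And if the products are truly equal, a test at margin .08 and one-sided 5% passes in only about 48%, 26%, 19% and 12% of trials (ψ = .13, .30, .50, 1.0). Finally, this is a minimal-risk, single-visit study, and no safety conclusion depends on the point.

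**Conclusion.** The concern holds and must be fixed, because it affects the only primary objective: the analysis named in section 8.4 does not test it. This conclusion comes from the text alone and needs no assumption. The size does need assumptions, namely the preference share, uncorrected McNemar, Wald bounds and, for power, differences favouring Spectrum. Under these, reading non-significance as success would pass a .08 deficit in 69% to 94% of trials, against about 4% to 8% for a non-inferiority test at one-sided 5%. At a true advantage of .15, McNemar would detect Spectrum's lead in 14% to 45% of trials where the non-inferiority test passes 31% to 90% (ψ from 1.0 to .30). The gap is wider for the VAS scores, which have no margin anywhere and no rule for combining them with preference.

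**What to change.** - **Section 8.4.2:** make the primary preference analysis a paired non-inferiority test. State the hypothesis, and compare the lower confidence bound of the proportion preferring Spectrum minus the proportion preferring Purell with one margin at one stated one-sided alpha. Take the margin from the .03 to .08 range, justify it, and fix it and alpha before data are seen. Name the interval method; a score-based paired bound is worth considering given how Wald behaves at low preference shares.
- **Section 8.4.1:** the simpler course is to designate preference, the only sized measure, as the single primary measure and make both VAS scores supportive, with the endpoint text in the Synopsis and section 3 amended to match. Otherwise set a margin in mm for satisfaction and for moisturization, compare each with the lower bound of the within-participant mean difference, and say whether all measures must pass.
- **McNemar and t-tests** may stay as superiority tests after non-inferiority is shown.
- **Section 8.1 and the Synopsis:** restate the 80% power with the chosen margin, alpha, direction of difference and assumed preference share.

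The cost is wording and a few sponsor decisions, with no new data items. The restated power may be less favourable than 80%, and the sponsor should know that before enrolment. Enlarging the trial is not part of this change.
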